9.1.2 Secondary outcomes

Changes in HbA1c from baseline to 6-months follow-up (week 48) between and within the two study groups (BCC and control).

Changes from baseline to the end of the intervention period (week 24) and at 6-month follow-up (week 48) between and within the two study groups (BCC and control) in:

- Body weight
- Blood pressure
- Lipid profile: low-density lipoprotein cholesterol (LDL-C), high-density lipoprotein cholesterol (HDL-C), total cholesterol (TC), free fatty acids (FFA) and triglycerides (TG)
- Waist and hip circumference
- Mathematical literacy
- Carbohydrate estimation accuracy
- Self-reported diet-related quality of life, perceived competencies in diabetes, health-care climate and physical activity

Changes from baseline to the end of the intervention (week 24) between and within study groups in:

- Other parameters of plasma glucose variability including time in range (3.9-10.0 mmol/l), % time spent in hypoglycaemia (<3.9 mmol/l), % time spent in hyperglycaemia (e.g. >11.1 mmol/l) and standard deviation of mean plasma glucose
- Body composition
- Dietary intake (total energy, intake of carbohydrate, fat, protein, added sugar and dietary fibre)

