13.3 Determination of sample size

Allowing for drop-outs (~30%) and subgroup analyses we plan to include a total of 226 patients in our study. This is based on sample size calculations which suggested that including 87 participants in each of the study groups would give us 80% power to detect a clinically meaningful difference in change in HbA1c of 3.0 mmol/mol between the BCC group versus the control group with a 5% significance level using a two-sided test and an estimated standard deviation (SD) of 7 mmol/mol. This SD and dropout rate have previously been used for sample size calculations and were similar to what we found when evaluating our BCC courses on dropout rate, mean changes and SD of HbA1c after 6 months in completers with T2D. MAGE has only been used as an outcome measure of glucose variability in a few randomized controlled dietary intervention studies of patients with diabetes (40, 41) showing differences in changes in MAGE up to 4.8 mmol/l (SD: 1.0) after a 12-week carbohydrate counting intervention (40). By including 113 participants in each study group we will have a power of 80% (alpha level of 0.05) in a two-sided test to detect a clinically meaningful difference in the change in MAGE during the intervention period (24 weeks) of \geq 0.30 mmol/l (SD 0.7 mmol/l) between the study groups as presented in **Table 5**.

Difference in HbA1c, mmol/mol (SD 7.0)	Difference in MAGE, mmol/l (SD 0.7)	Net no of participants in the study (BCC vs control)	No of participants given a dropout rate of 30%
2.0	0.20	388	504
3.0	0.30	174	226
3.5	0.35	128	166
4.0	0.40	100	130

Table 5: Sample size calculations

14 Data management

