Estimation of minimal important difference for primary outcome: Reductions in HbA1c of 3 mmol/mol and 0.3 mmol/l of MAGE were defined as minimal important differences in this trial. This was primarily based on findings from clinical trials of different dietary approaches for reducing HbA1c in T2D (18, 19). Since no studies had examined the effect of dietary interventions using MAGE as an outcome in our target population with T2D at the time. Thus, based on previous findings (18, 19) we expected to find HbA1c reductions around 3 mmol/mol compared to standard care. This was considered clinically relevant as part of a multidisciplinary approach for the management of hyperglycaemia in T2D.

Secondary/descriptive/exploratory outcomes

The treatment effect will be given as the baseline corrected difference between the groups at V2 and V3. No minimal clinically relevant differences were defined for these outcomes.

- HbA1c (mmol/mol) (only for V3)
- Total body weight (kg), women
- Total body weight (kg), men
- BMI (kg/m²)
- Blood pressure
 - Systolic blood pressure (mmHg)
 - Diastolic blood pressure (mmHg)
- Fasting concentration of plasma lipids
 - Total cholesterol (mmol/l)
 - LDL cholesterol (mmol/l)
 - HDL cholesterol (mmol/l)
- Anthropometry
 - Waist circumference, cm (women)
 - Waist circumference, cm (men)
 - Waist/Hip ratio, unitless (women)
 - Waist/Hip ratio, unitless (men)
- Blinded CGM data (not measured at V3)
 - Mean plasma glucose, mmol/l
 - Time in range (TIR): % of readings and time 3.9-10.0 mmol/l
 - Time above range (TAR): % and readings and time 10.1-13.9 mmol/l
 - Time below range (TBR): % readings and time 3.0-3.8 mmol/l
 - Glycaemic variability, coefficient of variation (CV), %
 - Glycaemic variability, standard deviation (SD), mmol/l
- Numeracy skills test

- Total score
- Correct answers, n and %
- Carbohydrate estimation accuracy test based on 11 high-carb foods (only for foods reported eaten)
 - Estimation errors in %
- Self-reported diabetes diet-related quality of life (DDRQOL), total score within each subscale
 - General perception of diet
 - Satisfaction with diet
 - Restriction of social functions
 - Burden of dietary therapy
 - Perceived benefits of dietary therapy
 - Mental health
 - Vitality
- Self-reported Perceived Health Competence Scale (PCS), total score
- Self-reported Healthcare Climate Questionnaire (HCCQ) (not measured at V3), total score
- Dietary intake (not measured at V3)
 - Total energy intake (kJ/day)

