 - Carbohydrate intake (E%)
 - Total fat (E%)
 - Protein (E%)
 - Alcohol (E% and units/day) (women)
 - Alcohol (E% and units/day) (men)
 - Saturated fat (g/day) (women)
 - Saturated fat (g/day) (men)
 - Monounsaturated fat (g/day) (women)
 - Monounsaturated fat (g/day) (men)
 - Polyunsaturated fat (g/day) (women)
 - Polyunsaturated fat (g/day) (men)
 - Dietary fibre (g/day and g/10 MJ) (women)
 - Dietary fibre (g/day and g/10 MJ) (men)
 - Added sugar (g/day and g/10 MJ) (women)
 - Added sugar (g/day and g/10 MJ) (men)
- Self-reported physical activity (International Physical Activity Questionnaire – Short Form (IPAQ SF))
 - MET-minutes/week
 - Low, n and %
 - Moderate, n and %
 - High, n and %

Other outcomes

Number of visits with dietitians, endocrinologists, and diabetes nurses at V2 and V3 in each group.

Supplementary table with baseline characteristics for completers vs. non-completers with dropout before V2

- Number of participants, n
- Age (years)

- Gender, male, n and %
- Ethnicity, white, n and %
- Current smokers, n and %
- Self-reported educational level
 - Elementary school, n and %
 - Upper secondary education, n and %
 - Vocational, n and %
 - Short further (< 3 y), n and %
 - Medium further (3-4 y), n and %
 - Long further (> 4 y), n and %
 - Other education, n and %
- Living alone, n and %
- Body weight (kg), female
- Body weight (kg), male
- BMI, kg/m²
- Diabetes duration (years)
- HbA1c (mmol/l)

Analysis methods

Analyses of the primary outcomes will be performed based on efficacy estimates.

Adjustment for relevant confounders will be performed including adjustment for design variables used for stratified randomization based on the participants' gender, BMI and HbA1c at baseline.

Before further analysis and before unblinding, all variables will be inspected to detect outliers to uncover potential errors, such as registration errors.

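### Nine secondary or exploratory outcomes, including body weight, are listed only by sex, and no combined treatment effect or sex-by-treatment test is planned

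*SAP*

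**What the plan says.** **Protocol.** Section 9.1.2 lists the secondary outcomes as comparisons between and within the two study groups. Body weight and waist and hip circumference come under "Changes from baseline to the end of the intervention period (week 24) and at 6-month follow-up (week 48"). Dietary intake, including added sugar and dietary fibre, comes under the list that runs to week 24 only. Neither list is divided by sex.

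**SAP.** Section 6 says that the treatment effect for the secondary, descriptive and exploratory outcomes is the baseline-corrected difference between groups at V2 and V3. Nine outcomes then appear only in sex-specific lines:

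- body weight ("Total body weight (kg), women", followed by the same line for men)
- waist circumference ("Waist circumference, cm (women") and a men's line)
- waist/hip ratio
- alcohol
- saturated fat ("Saturated fat (g/day) (women") and a men's line), monounsaturated fat and polyunsaturated fat
- dietary fibre
- added sugar

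BMI, blood pressure, lipids, total energy, carbohydrate, total fat and protein each have one line for everyone.

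The planned model has Visit and Visit-by-Treatment as fixed effects. The same section plans adjustment for the stratification variables, of which sex is one. Additional analyses are marked as not relevant. Section 4 applies Benjamini-Hochberg control at 5% to the secondary outcomes.

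**The concern.** Followed as written, the list gives two treatment effects for body weight, one in women and one in men, and none for the randomised groups as a whole. The same is true of waist, dietary fibre and added sugar, which the protocol also defines for the whole groups. Each estimate would then rest on only part of the sample.

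Two things are at stake. One is precision: a real effect of moderate size could be missed in both sexes although the full sample would have shown it. The other is interpretation: with two tests of modest power, a common effect will often reach significance in one sex and not in the other. No interaction test is planned that would show such a pattern to be chance.

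The documents give no reason for the split and no sex-specific hypothesis. Sex differences in level do not require it, because the model is baseline-corrected and adjustment for sex is already planned. The SAP itself treats total energy intake differently: it is split by sex in the baseline table and pooled as an outcome.

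**Working it through.** **1. Reproduce the plan's own figure.** The inputs in Protocol 13.3 are a target HbA1c difference of 3.0, an SD of 7 (both in mmol/mol), two-sided alpha 0.05 and power 80%. The stated result: "including 87 participants in each of the study groups would give us 80% power to detect a clinically meaningful difference in change in HbA1c".

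n per group = 2 × (1.960 + 0.842)² × (7/3)² = 2 × 7.851 × 5.444 = 85.5, rounded up to 86. The t-based solution is 86.4, rounded up to 87. Power at 87 per group is 80.7% by the normal approximation. The figure of 87 is reproduced.

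**2. Standard error in one sex.** For a difference between two means with n per arm, SE = σ√(2/n). If a sex makes up a share f of each arm, SE = σ√(2/(nf)). The ratio to the pooled SE is 1/√f, assuming the same residual SD in both sexes.

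**3. Power in one sex for an effect with 80% pooled power.** By the normal approximation, power = Φ(2.802 × √f − 1.960). The t-test figures use 79 per arm, which is 113 × 0.7 = 79.1.

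| Share f | SE ratio | Normal approximation | t-test |
|---|---|---|---|
| 0.35 | 1.69 | 38.1% | 37.4% |
| 0.40 | 1.58 | 42.5% | 41.9% |
| 0.50 | 1.41 | 50.8% | 50.3% |
| 0.60 | 1.29 | 58.3% | 58.0% |
| 0.65 | 1.24 | 61.7% | 61.5% |

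The documents do not give the sex ratio, so f is an assumption. The two shares must add to 1, so a gain for one sex is a loss for the other. The results hardly depend on the starting sample size.

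**4. Illustration on the protocol's own scale.** The documents give no effect size or SD for the nine outcomes, so this borrows the HbA1c standardised effect, 3/7 = 0.43, with 87 per arm (normal approximation).

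| Analysis | n per arm | Power | Detectable difference (80% power) |
|---|---|---|---|
| All participants | 87 | 81% | 0.42 SD |
| One sex, 50% share | 43.5 | 52% | 0.60 SD |
| One sex, 30% share | 26.1 | 34% | 0.78 SD |
| One sex, 70% share | 60.9 | 66% | 0.51 SD |

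**5. Chance of a one-sex-only result.** Suppose the effect is the same in both sexes and each test has 50% power. The chance that exactly one reaches p<0.05, before FDR correction, is 2 × 0.5 × 0.5 = 50%.

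**6. Which of the nine are protocol outcomes.** Set against Protocol 9.1.2, four are named there: body weight, waist circumference, dietary fibre and added sugar. Five are not: waist/hip ratio, alcohol, and saturated, monounsaturated and polyunsaturated fat. The protocol's fat intake survives in the SAP as pooled total fat.

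**The case against.** The strongest reply is that the SAP never says that models are fitted separately by sex. It describes one model for all continuous outcomes and plans adjustment for sex, which would be redundant inside a single-sex model. Similar women's and men's labels for weight, waist and waist/hip ratio appear in the descriptive baseline table, so the lines may be partly table layout. This stands as a limit on certainty. It does not remove the point: the SAP promises a treatment effect for the listed outcomes, and no combined line exists.

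Several stronger readings are tempting and are not supported:

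- **That all nine outcomes contradict the protocol.** Only four are named there.
- **That no whole-group test of weight change remains.** BMI is pooled, and Protocol 10.1 has height measured only at V1, so BMI change is weight change scaled by a fixed height. What is lost is the effect in kg. No pooled outcome does the same for waist.
- **That the FDR family grows from nine tests to eighteen.** That counts outcome names. Alcohol, fibre and added sugar carry two metrics each, and the weight and waist measures are estimated at two visits. The list's heading also does not say which items are secondary and which are exploratory.
- **That sex-specific estimates have no value.** Adjustment for sex does not deal with unequal residual variance, or with effects that differ between sexes in kg, cm or g/day. Showing both is defensible; the gap is the missing combined estimate.

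One could also argue that the sample size foresaw subgroups, since Protocol 13.3 says "Allowing for drop-outs (~30%) and subgroup analyses we plan to include a total of 226 patients in our study". But 174 × 1.3 = 226.2, so the dropout allowance accounts for the whole increase and nothing is left for smaller subsets.

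Finally, these outcomes have no minimal important difference and did not drive the sample size. That is fair and limits the severity.

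**Conclusion.** The point holds in limited form. On the literal reading of SAP Section 6, nine outcomes get sex-specific treatment effects only, with no combined estimate and no test of whether the effect differs by sex. For body weight, waist circumference, dietary fibre and added sugar, this leaves the comparison defined in Protocol 9.1.2 unestimated. For the other five it is a loss of efficiency and not a departure from the protocol.

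The size depends on a sex ratio that the documents do not give. With an equal split, the standard error is 1.41 times the pooled one and 80% power falls to about 50% in each sex; at 65:35 it falls to about 62% and 37%. These figures assume similar residual SDs in both sexes and an effect that would have had 80% power in the full sample.

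Severity is minor to moderate. Only secondary or exploratory outcomes are affected, and the HbA1c and MAGE analyses are unchanged.

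**What to change.** List each of the nine outcomes once. Analyse it in all participants with the planned baseline-corrected model, adding sex and sex-by-visit terms. Report that estimate as the treatment effect, and enter it in the FDR procedure wherever the outcome belongs to the secondary family.

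Keep the women's and men's estimates with confidence intervals as description. The sex-by-visit term only adjusts level over time and does not test whether the effect differs by sex. If a sex difference is to be discussed, base it on a sex-by-treatment-by-visit term, not on significance in one sex and its absence in the other. If residual variances differ by sex, allow a sex-specific covariance matrix.

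If the sex-specific lines were meant only as table layout, one sentence in the SAP saying so, together with a named combined analysis, settles the matter.

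The cost is SAP wording. No new data are needed, sex is already recorded and planned as an adjustment variable, and the sex-specific results can still be shown.

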Evidence suggest that a hands-on, learning-by-doing approach (problem- and experience-based patient education) can support the development of food skills in general, and improve diet quality in particular (32). Adding group-based dietary approaches to individual lifestyle counselling has also been found to improve dietary habits (33). Similarly adding diabetes self-management approaches to the diabetes education lead to lower dropout rates, increased self-efficacy and improved HbA1c in patients with T2D (34). This may be due to the fact that diabetes self-management education supports achieving personal goals for behaviour change that in turn could lead to better clinical outcomes.

The sparse scientific knowledge about the effect of BCC underlines the need for investigating and evaluating this in a practice-based group educational approach and examining the effect on improved metabolic control in patients with T2D.

In a small pre-post design study of 29 participants with T2D conducted at Steno Diabetes Center Copenhagen (SDCC) we found that patients offered a structured group education program in BCC improved their carbohydrate counting skills (p<0.001) and reported increased knowledge concerning types and amounts of carbohydrates and how to prevent hyper- or hypoglycaemia. However, no significant changes in HbA1c (p=0.08) or body weight (p=0.616) where found after six months (unpublished data). Despite the limited clinical effects in this small study the initial results are interesting and call for additional research in a stronger randomized set-up and with power to investigate whether a group-based dietitian-delivered program in BCC has an independent effect on glycaemic control and body weight management in patients with T2D in up to 12 months to assess if dietary adherence to the BCC program is still high after one year.

7 Main hypothesis

Training and education in the BCC concept will improve glycaemic control either by reducing HbA1c or the average plasma glucose variability more than offering a standard nutrition education (control) as a stand-alone dietary treatment. The underlying mechanisms are that nutrition education in BCC will improve the patients' knowledge and awareness of the ingested amount of carbohydrates, the accuracy of carbohydrate estimation together with focus on higher consistency (reduced variability) in the carbohydrate intake, all of which will reduce glucose variability and HbA1c.

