HbA1c was measured at the screening visit (V0), at the baseline visit (V1), after 12 weeks of intervention, after 24 weeks (V2) of intervention, and after six months follow-up (V3). MAGE was measured after the baseline visit (V1), and after 24 weeks of intervention (after V2).

See section 6: Analyses for timing of secondary and descriptive/explorative outcome assessments.

Section 4: Statistical Principles

Confidence intervals and P values

Two-sided P-values and 95% confidence intervals will be presented for comparisons between groups. Two-sided 95% confidence intervals will be presented for within group comparisons and estimated levels.

Primary outcome: The direction and size of the estimated mean effect for HbA1c and MAGE (primary outcomes), in addition to the 95% confidence intervals, will be required to support the tested hypothesis for the results to be declared in accordance with the hypothesis (see section 2 under “Objectives”).

Secondary outcomes: False detection rate (FDR) correction ad modum Benjamini and Hochberg (16) will be used to control for multiplicity; < 5% will be used as the threshold for FDR.

Completers and protocol deviations

Completers: Participants who participated in an assessment of at least one of the primary outcomes at V2 and/or V3.

Lost to follow-up: Participants who did not participate in assessment of primary outcomes at V2.

Excluded for statistical data analyses: Participants in both study groups dropping out or lost to follow-up before baseline measurements have been collected.

Protocol deviators: None of the participants in the two study groups are considered protocol deviators.

Analysis populations

Efficacy estimates based on intention-to-treat (ITT) analysis set:

All participants will be analysed as randomised.

Section 5: Trial Population

Screening data

The following data obtained at the screening visit will be included for those that entered the trial:

- Age
- Self-reported sex
- Self-reported ethnicity
- Self-reported educational level
- Self-reported smoking status and number of years of smoking
- Diabetes duration

Eligibility

- Age: ≥ 18 to ≤ 75 years
- Diabetes duration: ≥ 12 months
- HbA1c: 53–97 mmol/mol
- Diet or any glucose-lowering medication
- Diagnosed with T2D and treated at Steno Diabetes Center Copenhagen

Recruitment

The flow diagram of the trial will comply with the most recent CONSORT guidelines for Reporting Outcomes in Trial Reports and includes:

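### The SAP closes time above range at 13.9 mmol/l and time below range at 3.0 mmol/l, so the most extreme readings fall in no band and both measures can move the wrong way

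*SAP*

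**What the plan says.** SAP section 6, under blinded CGM data, lists three time measures. The middle one agrees with the protocol: "Time in range (TIR): % of readings and time 3.9-10.0 mmol/l". The one above it has a ceiling: "Time above range (TAR): % and readings and time 10.1-13.9 mmol/l". The one beneath has a floor: "Time below range (TBR): % readings and time 3.0-3.8 mmol/l".

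The baseline characteristics list in SAP section 5 uses the same limits. Neither list has a band above 13.9 or below 3.0 mmol/l, and the SAP section on additional analyses adds nothing.

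Protocol section 9.1.2 names the same kind of outcomes with open tails: "time spent in hypoglycaemia (<3.9 mmol/l), % time spent in hyperglycaemia (e.g. >11.1 mmol/l". The SAP gives no reason for closing them, or for starting the upper band at 10.1 instead of the protocol's example of 11.1.

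The SAP reports a baseline-corrected group difference for each measure and states that "No minimal clinically relevant differences were defined for these outcomes".

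**The concern.** A measure called time above range should not get worse when glucose gets better. With a ceiling at 13.9 mmol/l, it can. A reading that improves from 15 to 12 mmol/l enters the band and raises the measure. At the low end, a reading that worsens from 3.5 to 2.5 mmol/l leaves the band and lowers time below range. This follows from the definitions and needs no model.

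It bears on this trial because of the main hypothesis in protocol section 7: "Training and education in the BCC concept will improve glycaemic control either by reducing HbA1c or the average plasma glucose variability". Lower variability pulls readings in from the tails. Readings that come down from above 13.9 into 10.1-13.9 mmol/l are then scored as harm, so time above range could point against the intervention while the other measures favour it.

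**Working it through.** The plan gives no figure for these measures to reproduce. The check has a definitional part and an illustrative part.

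**1. Coverage.** Assigning every value from 2.0 to 25.0 mmol/l in steps of 0.1 to the SAP bands leaves exactly 2.9 and below, and 14.0 and above, unassigned.

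**2. Monotonicity, on 100 fixed readings.**

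- Upper band: with 60 readings at 8, 20 at 12 and 20 at 15 mmol/l, SAP time above range is 20%. Lowering the 15s to 12 (better) raises it to 40%. Raising half of the 12s to 15 instead (worse) lowers it to 10%. Time >10.0 is 40% in all three cases.
- Lower band: with 2 readings at 3.5 and 3 at 2.5 mmol/l, SAP time below range is 2%. Raising the 2.5s to 3.5 (less severe) raises it to 5%. Time <3.9 stays at 5%.

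**3. Identity.** Write TAR for the SAP band and T(>x) for time above x. Then TAR = T(>10.0) − T(>13.9), so ΔTAR = ΔT(>10.0) − ΔT(>13.9). Any fall in time >13.9 is subtracted from the benefit.

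**4. Size, under assumed distributions.** Assumptions: sensor glucose is lognormal or normal, SD = CV × mean, CV 20-36%. Because readings have one decimal, the band edges are 2.95, 3.85, 10.05, 11.15 and 13.95. For the lognormal, s² = ln(1 + CV²) and μ = ln(mean) − s²/2. Paired results below are lognormal / normal.

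*Share captured at constant CV*, that is ΔTAR ÷ ΔT(>10.0):

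- Mean 10 to 9: 53-86% / 40-90%.
- Mean 11 to 10: 39-69% / 8-63%.
- With edges at exactly 10.0 and 13.9, these limits shift by at most 2 percentage points.

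*Turning point.* At constant CV, TAR is highest at a mean of 10.7-12.6 mmol/l over both models. Above that it rises as the mean falls.

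*Against the protocol's example of >11.1* (lognormal, CV 28%):

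- Mean 9 to 8: TAR falls more (10.2 against 9.0 points), because its lower limit is 10.1.
- Mean 10 to 9: TAR falls less (9.6 against 11.7 points).
- The switch to understatement comes at a mean of 7.8-9.9 mmol/l over both models.

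*Falling variability, from mean 10 and CV 30%.* One case in full (lognormal, to mean 9.8 and CV 25%):

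- Before: s = 0.294, T(>10.0) = 43.5%, T(>13.9) = 10.0%, TAR = 33.5%.
- After: s = 0.246, T(>10.0) = 41.1%, T(>13.9) = 6.0%, TAR = 35.1%.
- Change: TAR +1.6 points, although T(>10.0) falls by 2.4.

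| Change in percentage points | Mean stays 10, CV to 25% | Mean to 9.8, CV to 25% |
|---|---|---|
| SAP TAR | +3.8 / +3.6 | +1.6 / +1.5 |
| Time >10.0 | +0.8 / −0.1 | −2.4 / −3.4 |
| Time >11.1 | −1.6 / −2.8 | −4.4 / −6.0 |
| Time in range | −0.7 / +1.5 | +2.5 / +4.7 |

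With this fall in CV from a mean of 10, TAR rises unless the mean falls to about 9.66 / 9.67, a drop of 0.34 / 0.33 mmol/l.

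*Uncounted time at mean 10.* Time >13.9 is 2.4-13.6%, and the three SAP bands sum to 83.9-97.6% over both models.

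*Low end at mean 8.* Time <3.0 depends heavily on the model: 0.02% (CV 28%) and 0.36% (CV 36%) lognormal, against 1.2% and 4.0% normal.

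**The case against.** The strongest reply is that little depends on these measures. They are secondary, descriptive or exploratory, have no minimal relevant difference, and play no part in the superiority rule. HbA1c, MAGE, time in range, mean glucose, SD and CV use every reading. A reader can also nearly recover the uncapped point estimate, since 100 − TIR − TBR equals time >10.0 plus time <3.0. All of this stands and limits the weight of the point. The recovered figure would, however, mix the two tails and come without a confidence interval.

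Second, the protocol is not a clean standard. Its limits leave 10.1-11.1 mmol/l in neither time in range nor hyperglycaemia, and its upper limit is only an example. Both are true. Its tails are open all the same, so its two tail measures are monotone. At the low end the change is firm, from "time spent in hypoglycaemia (<3.9 mmol/l" to 3.0-3.8 mmol/l.

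Third, the reversal depends on the starting point. TAR falls in each of these nearby cases (lognormal / normal):

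- Mean 9 to 8.8, CV 30% to 25%: by 1.9 / 4.0 points.
- Mean 10 to 9.5, CV 30% to 28%: by 3.1 / 2.9 points.
- Mean fixed at 8.5, CV 30% to 25%: by 0.9 / 2.8 points.

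These figures are right, and a reversal should not be presented as likely. When variability alone falls at a mean of 10, the lognormal model also has time >10.0 rising and time in range falling slightly, so open-ended limits do not remove every conflict of sign. They do ensure that no single improving reading counts as harm.

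**Conclusion.** The point holds. Followed as written, the SAP would report measures labelled time above and time below range that omit the most extreme readings and are not monotone. That conclusion is definitional and certain.

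The size is illustrative, because the documents give no CGM distribution. The main expected effect is attenuation of the time-above-range result relative to all time >10.0. Against >11.1 the direction depends on the mean. A reversal for a whole group is possible but not expected. The flaw in time below range is one of definition, and no material size is claimed for it.

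The primary conclusions on HbA1c and MAGE are untouched. The definitions should be corrected because these are protocol-listed outcomes with a reported group difference, and the correction is cheap.

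**What to change.** Define time above range as all time >10.0 mmol/l and time below range as all time <3.9 mmol/l, and leave time in range at 3.9-10.0, so that the three sum to 100%. Report >13.9 and <3.0 mmol/l as sub-bands; the SAP's present bands then remain available by subtraction. Use the same definitions in the baseline table and the outcome list. State whether the protocol's example of >11.1 mmol/l is kept or replaced, and why the SAP departs from section 9.1.2.

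As a separate clarification that adds no weight here, say whether these two measures belong to the family to which this applies: "False detection rate (FDR) correction ad modum Benjamini and Hochberg (16) will be used to control for multiplicity".

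The cost is SAP wording and a recomputation from CGM data already collected. If results have already been seen, report both definitions and date the change.
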